## **V. WATERBIRTH PROTOCOL**

*This protocol is taken directly from the American College of Nurse-Midwife's 'A Model Practice Template for Hydrotherapy in Labor and Birth' (2016)*

### **A. Management of labor in water**

1. Before immersion, ensure that the woman is a candidate for warm water immersion based on inclusion and exclusion criteria
  - a.) The tub should be filled using ordinary tap water without additives (e.g., salt, essential oils, sanitizers).
  - b.) The water temperature should be assessed and documented hourly by nursing.
  - c.) During the first stage of labor in water, the water temperature should never exceed 37.7°C (100°F) and may be adjusted to cooler temperatures per the woman's preference.
2. The woman in labor may enter or leave the water at any point with assistance.
  - a) The woman should be instructed to use proper body mechanics when entering and exiting the tub and do so only with staff or a support person in attendance.
  - b) If complications or changes occur in the maternal or fetal condition that require further assessment or treatment outside of the tub, share this information with the family and assist the woman out of the tub.
3. Positioning for comfort in the tub is dependent on the preferences of the woman and the judgment of the provider in consultation with the woman.
4. Provide hydration in the form of oral liquids or intravenous (IV) fluids as indicated. All IV or saline lock sites should be covered with an occlusive, water-resistant dressing while the woman is in the tub.
5. The well-being of the woman and fetus are assessed and managed in accordance with practice protocols for *any other woman* during labor, including monitoring maternal vital signs, assessing the fetal heart rate and initiating intrauterine resuscitation strategies when indicated (e.g., maternal position changes and IV fluid bolus for fetal heart rate changes or Category II fetal heart rate).

- a.) A waterproof Doppler or waterproof electronic fetal monitoring equipment should be used to assess the fetal heart rate.
- b.) Waterproof electronic fetal monitoring equipment may be used to verify or clarify if an indeterminate fetal heart rate pattern is present, and this can guide management.
- c.) Management of indeterminate fetal heart rate patterns depend on multiple factors. Intrapartum resuscitation techniques such as position change, hydration, and correction of hypotension or tachysystole are instituted as necessary.

## **B. Management of the second stage of labor**

1. The woman may choose any position in the tub or pushing during the second stage of labor that feels comfortable and that is deemed safe by the attending provider or registered nurse. The health care professional may request adjustments to the position to facilitate observation of progress and/or to maintain assessment of maternal and fetal wellbeing. Additionally, the health care professional will document that they are comfortable proceeding with the subject in the study once in the second stage of labor through a dot phrase (waterbirthsecondstage Appendix A).
2. Water temperature
  - a.) During the second stage of labor, the water temperature should never exceed 37.7°C (100°F) and may be adjusted based on the woman's preference within a narrow range of 36.1°C to 37.7°C (97.0°F to 100°F).
3. Maternal and fetal well-being should be assessed and documented as they would be for a conventional (land) birth
4. Fetal heart rate and contraction pattern are assessed in accordance with standard of care recommendations, generally every 5 to 15 minutes (in accordance with AWHONN/ACOG guidelines).
5. Supporting birth of the neonate
  - a.) The woman should be supported in the use of spontaneous, physiologic pushing.
  - b.) The health care provider may use a hands-off or hands-poised position to facilitate birth by controlled, spontaneous, pushing efforts; a hands-on method of birth management may be employed when indicated.
  - c.) It may not be necessary to feel for the presence of a nuchal cord if the birth of the body quickly follows the head. Loose nuchal cords and other entanglements can be resolved as the neonate is born underwater before the first breath
  - d.) The time of birth will be noted when the neonate's entire body is outside of the woman.
  - e.) The neonate must be born completely underwater without exposure to air until the face is brought gently and directly to the surface. The neonate's head **must not** be re-submerged under water after it has been brought to the surface.
  - f.) If a woman raises herself out of the water and exposes the head of the fetus to air, she should be assisted/supported to remain out of the water to avoid the potential risk of the neonate gasping underwater with re-submersion.
  - g.) After birth, assist in bringing the neonate directly and gently to the surface (within 5–10 seconds) to minimize tension on the umbilical cord and to reduce the possibility of avulsion. Cord clamps should be readily available.
  - h.) Maintain warmth of the neonate through skin-to-skin contact with the woman

and submersion of the neonate's lower extremities, abdomen, and chest. Dry the neonate's exposed head to reduce heat loss.

i.) Apgar scores should be obtained at one and 5 minutes after birth per routine standards.

j.) In the presence of stable newborn status and transition to extrauterine life, care of the cord can follow best practices to support delayed cord clamping.

k.) If neonatal resuscitation measures are indicated and this is not possible without cutting the cord the cord should be clamped and cut, and the neonate removed from the water immediately and brought to the infant warmer.

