We initially aimed to enroll 120 patients in the study, 80 enrolled within the waterbirth group and 40 in the land group. We recognize that some women will risk-out or opt-out because of the unpredictability of labor and birth. Additionally, we aim to approach most patients eligible for waterbirth with the understanding that some women will not want to participate in a research study. We have recalculated our sample sized based on the current enrollment attrition rate of 39.4% (rate in which patients risk out of the study). With a 2:1 allocation ratio, approximately 120 subjects were initially earmarked to be recruited into the study given 74 would be needed in the waterbirth and 37 would be needed in the land birth group to detect a 40% reduction in epidural use. Following the recommendations of Sakpal, we used the attrition rate (rate in which patients risk out of the study) to calculate adjusted sample sizes as 124 in the waterbirth group and 62 in the land birth group for a total of 186.

Participants who are ineligible for waterbirth will be excluded from both the land or water groups, and no further data will be collected. Please note that given the variable nature of birth, once a woman is randomized and enrolled to either group and meets ongoing eligibility criteria, an intention to treat model will be used for analysis following the birth.

Study participation will be offered to women seeking routine prenatal care in the Midwifery and Wellness Clinic, Exclusively for Women, and the Women's Health Clinic at Aurora Sinai Medical Center at the beginning of the third trimester (25 weeks 0 days to 34 weeks 0 days gestation). Eligible patients will be consented by a research study coordinator (risks and benefits will be done by an Aurora UW Medical Group midwifery or obstetric provider [CNM or physician] listed on this protocol) following the patient's prenatal visit. Note, in rare cases midwifery or obstetric providers listed on this protocol may conduct full consent. Following voluntary consent, all study participants will be randomized (see above for randomization).

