## VI. STANDARD LAND BIRTH PROTOCOL

Women randomized to the land birth group will be admitted to L&D as inpatients and will be cared for using routine standards of care, consistent with practice guidelines from ACNM/ACOG/AWHONN. Standard labor options (pain control, positioning, monitoring) will be offered to women in accordance with their particular labors and needs.

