## VII. STATISTICAL PLAN

The **primary outcome** we seek is a reduction of IV narcotic and epidural anesthesia use. We anticipate that this pilot project would be powered to detect a very clinically meaningful percentage point reduction in use of IV narcotic and epidural anesthesia. We carried out a power analysis using G\*Power 3.1.9.6. Using the Fleiss methodology to estimate power calculations with 80% power at the 0.05 level of significance, we estimate the following: to detect about 80% reduction in IV narcotic use from 24.5% down to 5.5%, estimated need would be 68 in the waterbirth group, 34 in the control group. To detect about 40% reduction in epidural use from 59% down to 34%, estimated need would be 74 in the waterbirth group, 37 in the control group. We have recalculated our sample sized based on the current enrollment attrition rate of 39.4%

(rate in which patients risk out of the study). With a 2:1 allocation ratio, approximately 120 subjects were initially earmarked to be recruited into the study given 74 would be needed in the waterbirth group and 37 would be needed in the land birth group to detect a 40% reduction in epidural use. Following the recommendations of Sakpal, we used the attrition rate (rate in which patients risk out of the study) to calculate adjusted sample sizes as 124 in the waterbirth group and 62 in the land birth group for a total of 186. We continue to approach most pregnant people eligible for waterbirth with the understanding that some will not want to participate in a research study. The results of this pilot should inform sample size required for a larger, definitive study that would be powered to detect smaller, still meaningful reductions in narcotic/epidural use.

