We will compare baseline characteristics and pre-determined outcomes between patients who are randomized to either waterbirth or land birth. We will compute frequencies, means with 95% confidence intervals, and medians with interquartile ranges, as appropriate per variable type. Differences among the groups will be tested using the Pearson chi-squared test of independence (or Fisher's exact), Student's t-test, or Wilcoxon's rank sum test, respectively. Continuous variables will be assessed for normal distribution. Categorical variables will be assessed for collinearity. Potentially, we will use logistic regression for binary categorical outcomes (e.g., opioid use/anesthetist intervention, maternal tears, vaginal birth versus conversion to cesarean section, etc.) and linear regression for continuous outcomes (e.g., blood loss, time to skin-to-skin contact, etc.). Potentially, we will also perform ordered logistic regression on ordinal outcomes such as satisfaction level and APGAR. All underlying assumptions will be tested for each statistical method used. A one tailed p value lower than 0.05 will be considered statistically significant.

Please note, a data safety monitoring plan has been created for this study and is included in Appendix D. The first ten subjects that are enrolled for a waterbirth will be monitored and reviewed by the study PI, co-investigators, and Maternal Newborn Quality Committee for any rare adverse outcomes. For all subjects, the Principal Investigator and co-investigators will continue to review all adverse outcomes and will regularly monitor the data to identify trends throughout the study.

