### ***.waterbirthsecondstage***

The subject is now in the second stage of labor. I \*\*\* am comfortable proceeding with the subject on the waterbirth study who was randomized to the waterbirth.

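### Beyond the admission strip, only the waterbirth arm has written in-labor checks tied to staying in the study, so women could be ruled out unequally by arm and the epidural comparison could be biased

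*Combined protocol and SAP*

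**What the plan says.** Section III lists the labor criteria (h to k) for all participants, including fetal heart tones on a 20-minute admission strip. Section IV makes later eligibility decisive: "Participants who are ineligible for waterbirth will be excluded from both the land or water groups", and data collection on them stops. It confines intention to treat to women who still meet the criteria.

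Within labor, the waterbirth protocol (section V) has two checks. Part A(1) reads "Before immersion, ensure that the woman is a candidate for warm water immersion based on inclusion and exclusion criteria". Part B(1) adds that "the health care professional will document that they are comfortable proceeding with the subject in the study once in the second stage of labor". The template for that note, .waterbirthsecondstage in Appendix A, has the provider state that they "am comfortable proceeding with the subject on the waterbirth study who was randomized to the waterbirth", so it cannot be completed for a land-arm woman.

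Section VI says that women in the land arm "will be admitted to L&D as inpatients and will be cared for using routine standards of care". It contains no study-eligibility step, note or trigger.

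Two other places bear on who is analysed. Section III, exclusion 2, lets the birth attendant exclude a woman at any time but keeps her in her randomized group. Section VII (Data Collection), item 1b, gives a wish to leave the water as an example of withdrawing participation, while item 2p records a switch from waterbirth to land birth as an ordinary variable.

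**The concern.** If ineligible women leave the analysis, whoever detects ineligibility decides who is analysed. The plan intends one criterion for both arms but, after admission, gives only one arm a step that prompts staff to apply it. Staff know the assignment, and nobody attending a land birth has to decide about immersion. Meconium-stained fluid, fever or a change in heart-tone category could then be recorded as study ineligibility in the waterbirth arm and managed as ordinary labor in the land arm.

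Women who fail labor criteria plausibly have more complicated labors and more epidurals. Removing more of them from the waterbirth arm would lower that arm's retained epidural rate without any treatment effect, in the direction of the primary hypothesis. The 39.4% risk-out rate that drives the target of 186 would also be a mixture of two differently measured quantities.

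**Working it through.** **The plan's own figure.** Section VII (Statistical Plan) gives a "reduction in epidural use from 59% down to 34%, estimated need would be 74 in the waterbirth group, 37 in the control group", "with 80% power at the 0.05 level of significance". The analysis rule is "A one tailed p value lower than 0.05 will be considered statistically significant". A one-sided two-proportion formula at 2:1 without continuity correction gives 36 land and 72 waterbirth, within one land and two waterbirth women of the stated 37 and 74. A two-sided version gives 46 and 92. Inflating for 39.4% gives 37/0.606 = 61.1, rounded up to 62, and 2 × 62 = 124, for a total of 186. The planned numbers therefore rest on a one-sided test and a single overall risk-out rate.

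**Bias with no true effect.** Let x be the share of an arm ruled out and r the epidural rate among ruled-out women, with 59% overall in both arms. The retained rate is (0.59 − x·r)/(1 − x).

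ASSUMPTIONS: x = 0.394 in waterbirth, x = 0.20 in land, r = 0.70 to 0.80. None of these by-arm values is in the documents.

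- r = 0.70: waterbirth (0.59 − 0.2758)/0.606 = 51.8%; land (0.59 − 0.14)/0.80 = 56.25%. False benefit 4.4 points.
- r = 0.80: waterbirth (0.59 − 0.3152)/0.606 = 45.3%; land (0.59 − 0.16)/0.80 = 53.75%. False benefit 8.4 points.
- r = 0.59: both arms retain 59%. No bias, whatever the shares.
- r = 0.50: waterbirth (0.59 − 0.197)/0.606 = 64.9%; land (0.59 − 0.10)/0.80 = 61.25%. A false disadvantage of 3.6 points.

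**Rejection probability.** Retained numbers are 124 × 0.606 = 75 and 62 × 0.80 = 50. With a normal approximation, rejection = Φ((d − 1.645·SE0)/SE1), where d is the false benefit, SE0 the pooled standard error and SE1 the unpooled one.

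- r = 0.70: (0.044 − 1.645 × 0.0912)/0.0910 = −1.16, giving 12%.
- r = 0.80: (0.084 − 1.645 × 0.0914)/0.0912 = −0.73, giving 23%.

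**Sensitivity to the use of 39.4%.** The documents give 39.4% as an overall rate. Placing it in the waterbirth arm with 20% in land implies (124 × 0.394 + 62 × 0.20)/186 = 32.9% overall. Holding the overall rate at 39.4% instead:

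| Land ruled out | Waterbirth ruled out | False benefit, r = 0.70 to 0.80 | One-tailed rejection |
|---|---|---|---|
| 20% | (0.394 × 186 − 12.4)/124 = 49.1% | 7.9 to 15.0 points | 21% to 48% |
| 30% | (0.394 × 186 − 18.6)/124 = 44.1% | 4.0 to 7.6 points | 11% to 20% |
| 39.4% | 39.4% | 0 | 5% |

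**A second parameterization.** Start from 37 land and 74 waterbirth women and remove an extra share from the waterbirth arm only. If those removed have 80% to 100% epidural use, one-tailed rejection is 7.8% to 11.5% for an extra 10% and 12.6% to 25.1% for an extra 20%. If they have 59%, it stays at 5.0%.

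**The case against.** A reader might infer that labor eligibility is assessed in the waterbirth arm alone and that the comparison is therefore tilted toward waterbirth. The documents do not support that.

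- **The criteria are common.** Criteria h to k, the exclusion note (.waterbirthexclusion) and the ineligibility reasons in item 1a carry no arm restriction, and section IV excludes from both groups. Section VI is silent; it does not say that land-arm women go unassessed. This stands, and it limits the point to the written steps after the admission strip.
- **The second-stage note is weak evidence.** It records provider comfort and does not re-check criteria. A refusal looks like a discretionary exclusion, and section III keeps such women in their group. It also comes late: women still proceeding in water at second stage probably include few with an epidural, so dropping them could move the bias the other way. This stands. The pre-immersion check carries most of the weight.
- **Size and direction are assumed.** No risk-out rate by arm is given. Randomization is at 25 to 34 weeks, so part of the 39.4% may be prenatal risk-out, which routine care would find in either arm. This also stands.
- **Complete follow-up would remove the problem.** If every randomized woman were analysed as randomized, unequal checking could not select the sample. That is right, and it belongs in the fix. Section IV as written does the opposite for criterion-based ineligibility, and the retention clause in section III covers only attendant discretion.

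**Conclusion.** The written in-labor checks tied to study status are asymmetric. Where section IV governs, that asymmetry can change who enters the primary comparison. The bias could run toward waterbirth, which is the plausible direction, but this is not established.

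Bias toward waterbirth, with the same kind of woman ruled out in each arm, needs two things together: more women ruled out in the waterbirth arm, and a higher epidural rate among them than among the rest. With both, the illustration gives 4.4 to 8.4 points against a planned effect of 25 (59% − 34%), and 12% to 23% rejection against a nominal 5%. Without the second, there is no bias; with lower epidural use among ruled-out women, the sign reverses. Equal shares would not by themselves guarantee balance if different kinds of women were removed in each arm.

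The change is worth making before the analysis because the safeguard is cheap and a differential exclusion cannot be repaired once outcome data have not been collected.

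**What to change.** 1. Make study eligibility in labor one assessment at one time point in both arms: at L&D admission, after the 20-minute strip, with the same date- and time-stamped note. Add the step to section VI.
2. Reword section V, B(1) and .waterbirthsecondstage so that the note concerns continuing in the tub, captured under item 2p, and not staying in the study. This changes the study status attached to the note and no clinical decision. Align item 1b with it.
3. Reconcile section III, exclusion 2 (retained by intention to treat) with section IV (excluded, no data), so that epidural and IV narcotic use are collected and analysed for every randomized woman. Any eligible-only analysis becomes secondary. Without this step, items 1 and 2 reduce the risk but do not remove it.
4. Report ineligibility by arm, reason and timing.

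**Cost.** Items 1, 2 and 4 need protocol wording, one shared note and one timed REDCap field, plus a short extra note for land-arm women. Item 3 uses data already in the delivery record but dilutes the effect. If ruled-out women have 59% epidural use in both arms, the waterbirth rate becomes 0.606 × 34% + 0.394 × 59% = 43.9%. The difference is then about 15 points, and one-sided power with 62 and 124 women is about 62%. The plan should state that openly.

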### **C. Management of the third stage of labor**

1. Although the third stage of labor may occur in or out of the tub depending on the status of the woman and neonate, provider skill and comfort, and duration of third stage, for the purpose of this study ***the third stage will be managed outside of the water.*** In rare cases, this may not be possible and the reason will be documented.

a.) The woman will be assisted out of the water and to the bed. Her infant may remain skin to skin or may be handed to a staff member while she moves to the bed. The infant will be placed skin-to-skin when she is in the bed.

b.) Quantified blood loss (QBL) will begin after the birth of the placenta, per routine unit standards.

c.) Inspection of the perineum and vagina for lacerations will occur in the bed per routine unit standards

### **D. Evaluation and care of the neonate**

a.) The neonatal resuscitation (NRP) guidelines of the American Heart Association should be utilized to assess the neonate and Apgar scores should be obtained at one and 5 minutes after birth per routine. If neonatal resuscitation measures are indicated and this is not possible without cutting the cord, the cord should be clamped and cut, and the neonate removed from the water immediately.

b.) Make certain the neonate remains close to the woman (skin-to-skin) and partially submerged to help maintain body temperature. Dry the neonate's exposed head to reduce heat loss.

c.) If neonatal tachycardia (heart rate greater than 160 bpm), bradycardia (heart rate less than 100bpm), hyperthermia (temperature greater than 38°C [100.4°F]), hypothermia (temperature less than 36°C [97.0°F]), tachypnea (respirations greater than 60 per min), grunting, or retracting is noted, the neonate should be moved to the infant warmer for further assessment, per routine unit standards.

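### The neonatal hypothermia trigger pairs 36°C with 97.0°F, which are different temperatures, so an infant in a 0.11°C band meets one limit and misses the other

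*Combined protocol and SAP*

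**What the plan says.** Section V (Waterbirth Protocol), part D, item c, gives heart rate, temperature and breathing findings for the newborn. If any is noted, "the neonate should be moved to the infant warmer for further assessment, per routine unit standards". The low-temperature finding is "hypothermia (temperature less than 36°C [97.0°F". The high-temperature finding in the same sentence is "hyperthermia (temperature greater than 38°C [100.4°F".

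Part B, item 2, sets the second-stage water temperature "within a narrow range of 36.1°C to 37.7°C (97.0°F to 100°F". It concerns water, not the newborn, but it is the only other place where the protocol uses 97.0°F, and there the Celsius partner is 36.1°C.

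The documents do not say which scale governs the newborn trigger.

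**The concern.** A limit printed on two scales should be one temperature. Here it is two, and the item is an operative rule, not background text. In a narrow band, a reader who applies the Celsius figure leaves the infant where it is, and a reader who applies the Fahrenheit figure moves it to the warmer.

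Item b of the same part asks staff to keep the newborn skin-to-skin with the mother, so the trigger also decides when that instruction gives way. Section VIII says the team hopes other hospitals will take up its protocols, so an uncorrected pair could be carried to other sites.

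**Working it through.** **Inputs**
- Newborn hypothermia trigger: below 36°C, bracketed as 97.0°F (Section V, part D, item c).
- Newborn hyperthermia trigger: above 38°C, bracketed as 100.4°F (same sentence).
- Second-stage water range: 36.1°C to 37.7°C, given as 97.0°F to 100°F (Section V, part B, item 2).

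**Formulas:** F = C × 9/5 + 32; C = (F − 32) × 5/9.

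**Step 1. Try to reproduce the plan's pair.**
- 36 × 9/5 + 32 = 64.8 + 32 = 96.8°F, not 97.0°F.
- (97.0 − 32) × 5/9 = 65 × 5/9 = 36.11°C, not 36°C.

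The pair is reproduced neither exactly nor to 0.1 degree. It is reproduced only by rounding to a whole degree: 96.8 becomes 97, or 36.11 becomes 36. Either direction works, so the arithmetic does not show which figure came first.

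**Step 2. Check the neighbouring pairs.**

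| Printed pair | Celsius converted | Fahrenheit converted | Agreement |
|---|---|---|---|
| 38°C / 100.4°F | 100.4°F | 38.0°C | exact |
| 36.1°C / 97.0°F | 96.98°F | 36.11°C | to 0.1 degree |
| 37.7°C / 100°F | 99.86°F | 37.78°C | loose; 37.78 rounds to 37.8 |
| 36°C / 97.0°F | 96.8°F | 36.11°C | not to 0.1 degree |

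**Step 3. Size of the gap.** 97.0 − 96.8 = 0.2°F, and 0.2 × 5/9 = 0.11°C.

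**Step 4. Who is classified differently.**

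| True temperature | Below 36°C? | Below 97.0°F? |
|---|---|---|
| under 36.00°C (under 96.8°F) | yes | yes |
| 36.00°C to just under 36.11°C (96.8°F to just under 97.0°F) | no | yes |
| 36.11°C (97.0°F) and above | no | no |

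The disagreement runs one way: only the Fahrenheit figure triggers.

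**Step 5. Readings to 0.1 degree.**
- A reading of 36.0°C is not below 36°C, but it converts to 96.8°F, which is below 97.0°F.
- Readings of 96.8°F and 96.9°F are below 97.0°F, but they convert to 36.00°C and 36.06°C, which are not below 36°C.
- A reading of 36.1°C converts to 96.98°F, shown as 97.0°F, so at that resolution neither limit is met.

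The documents give no distribution of newborn temperatures, so no count of affected infants can be calculated.

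**The case against.** The strongest reply is that the protocol converts loosely elsewhere. Its 37.7°C/100°F pair, used in parts A and B of Section V, is also inexact, and 97.0°F is what 96.8°F becomes when rounded to a whole degree. This is a fair point. A reader might infer from the exact 38°C/100.4°F pair that rounding is ruled out and that one figure must be a slip. The documents do not support that. Rounding may be the cause, but it would explain the mismatch without removing it: two limits are still printed, and they still disagree in the band. The same holds if the pair was inherited from the practice template from which Section V says it is taken, which cannot be checked here.

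A second reply is that the action is mild and surrounded by other guidance. The move leads only to further assessment under the unit's routine standards, neonatal resuscitation guidelines apply, clinical judgment is expected, and low temperature is one of seven listed findings. This limits the consequence. None of it says which temperature applies.

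A third reply concerns the trial's outcomes, and it stands. A reader might infer that the mismatch distorts the neonatal safety comparison under Hypothesis 4a, because a transfer could be counted as a complication. Neither newborn temperature nor transfer to the warmer is among the newborn variables in Section VII (Data Collection). Only the open field for other complications could capture it, and nothing says that it would. Nor is an effect on the skin-to-skin outcome shown. The variable is time from birth to contact, and part B (item 5h) has contact maintained in the tub after birth, so a later move need not change it.

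**Conclusion.** The contradiction is real and small. The hypothermia trigger in Section V, part D, item c, is printed as two temperatures 0.11°C (0.2°F) apart, and the documents do not reconcile them. The effect is confined to infants from 36.00°C to just under 36.11°C, for whom the Fahrenheit figure calls for transfer and the Celsius figure does not.

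The band follows from unit conversion alone and needs no outside figure. It takes both printed values literally, as strict lower limits. That few infants fall in the band is a judgment from its width, not a calculated result. Whether staff would in practice act differently depends on which figure they read, and the documents are silent on that.

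No effect on the primary outcome, the sample size or Hypothesis 4a is shown. No view is taken on which temperature is clinically right. The point merits an editorial correction because the figure is an action threshold for newborns.

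**What to change.** Reconcile the two figures in Section V, part D, item c, so that the Celsius and Fahrenheit values express the same temperature to the precision printed. The sponsor's clinicians should confirm which threshold is intended. The water-temperature pair in part B shows how 97.0°F is converted elsewhere in the protocol, but it is not evidence for either newborn threshold.

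The cost is one corrected figure in the next amendment. No analysis, sample size or data collection item changes.
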